5.1.8 Incompatibilities

In vitro studies suggest that trametinib dimethyl sulfoxide is not a substrate of CYP enzymes or of human BCRP, MRP2, OATP1B1, OATP1B3, OATP2B1, OCT1 or MATE1 transporters. Trametinib elimination by deacetylation to metabolite M5 is dependent on carboxylesterases (CES1b, CES1c and CES2). M5 is eliminated by CYP3A4 and other pathways, presenting the clinically relevant, albeit low, potential for drug-drug interaction. Trametinib is a substrate for P-gp and BSEP, but this is not expected to be clinically relevant due to trametinib's high permeability.

Trametinib dimethyl sulfoxide is an *in vitro* inhibitor of CYP 2C8, and is anticipated to have overall low potential for drug interactions as a perpetrator. It is also a weak CYP3A4 inducer and expected to have little clinical effect on sensitive substrates. Trametinib is not an inhibitor of CYP 1A2, 2A6, 2B6, 2C9, 2C19, 2D6 and 3A4 and not an inhibitor of P-gp, BCRP, OATP1B1, OATP1B3, OAT1, OAT3, OCT2, MRP2 and MATE1.

5.1.9 Side Effects

See Section [3.3](#) for side effects.

Appendix I

Rev. 12/16, 3/17

Patient Pill Calendar

Pill Calendar Directions

1. Take your scheduled dose of each tablet.
2. If a dose of trametinib is missed, only take the dose if it is more than 12 hours until the next scheduled dose.
3. Please bring the empty bottle or any leftover tablets and your pill calendar to your next clinic visit.
4. Take trametinib (GSK1120212) once daily by mouth either 1 hour before or 2 hours after a meal.
5. Trametinib should be stored at 2-8°C (36-46°F). Refrigerate. Do not freeze.
6. Trametinib should not be crushed, dissolved, or chewed.
7. Do not take an additional dose as a replacement if vomiting were to occur after a dose of trametinib.

Patient Pill Calendar

This is a calendar on which you are to record the time and number of tablets you take each day. You should take your scheduled dose of each tablet. **Note the times and the number of tablets that you take each day.** If you develop any side effects, please record them and anything you would like to tell the doctor in the space provided. Bring any unused tablets and your completed pill calendar to your doctor's visits.

Trametinib

DAY	Date			Time tablets taken	Use the space below to make notes about things you would like to tell the doctor (including unusual symptoms you experience, other medicine you have taken and anything else you think would be of interest.)
	Month	Day	Year		
1					
2					
3					
4					
5					
6					
7					
8					
9					
10					
11					
12					
13					
14					
15					
16					
17					
18					
19					
20					
21					
22					
23					
24					
25					
26					
27					
28					

Patient Signature: _____ Date: _____

Rev.2/16
Rev. 5/16,
Add13

**Molecular Analysis for Therapy Choice (MATCH)
MATCH Treatment Subprotocol R: Trametinib**

Appendix II

BRAF non-V600 Mutations Eligible for Inclusion

Gene Name	Variant ID	Variant Type	Variant Description	Level of Evidence Code
BRAF	COSM1739329	SNV	p.L485W	2
BRAF	COSM478	SNV	p.K601E	3
BRAF	COSM6265	SNV	p.K601N	3
BRAF	COSM472	SNV	p.T599I	3
BRAF	COSM21549	SNV	p.A598V	3
BRAF	COSM1126	SNV	p.L597S	3
BRAF	COSM1125	SNV	p.L597Q	3
BRAF	COSM471	SNV	p.L597R	3
BRAF	COSM470	SNV	p.L597V	3
BRAF	COSM469	SNV	p.G596R	3
BRAF	COSM53198	SNV	p.F595L	3
BRAF	COSM468	SNV	p.F595L	3
BRAF	COSM21612	SNV	p.F595L	3
BRAF	COSM466	SNV	p.D594V	3
BRAF	COSM253330	SNV	p.D594E	3
BRAF	COSM144576	SNV	p.D594H	3
BRAF	COSM467	SNV	p.D594G	3
BRAF	COSM211600	SNV	p.D594N	3
BRAF	COSM1583010	SNV	p.D594A	3
BRAF	COSM27639	SNV	p.D594N	3
BRAF	COSM463	SNV	p.E586K	3
BRAF	COSM462	SNV	p.N581S	3
BRAF	COSM1133046	SNV	p.Y472C	3
BRAF	COSM459	SNV	p.G469V	3
BRAF	COSM460	SNV	p.G469A	3
BRAF	COSM461	SNV	p.G469E	3
BRAF	COSM451	SNV	p.G466V	3
BRAF	COSM453	SNV	p.G466E	3
BRAF	COSM452	SNV	p.G466A	3
BRAF	COSM253328	SNV	p.G466R	3
BRAF	COSM449	SNV	p.G464E	3
BRAF	COSM450	SNV	p.G464V	3
BRAF	COSM1448615	SNV	p.G464R	3

Gene Name	Variant ID	Variant Type	Variant Description	Level of Evidence Code
BRAF	COSM1111	SNV	p.G464R	3
BRAF	COSM448	SNV	p.L463S	3
BRAF	COSM447	SNV	p.R462I	3
BRAF	AGAP3-BRAF.A9B9	Gene Fusion	BRAF Translocation	3
BRAF	AGAP3-BRAF.A10B11	Gene Fusion	BRAF Translocation	3
BRAF	AGK-BRAF.A2B8	Gene Fusion	BRAF Translocation	3
BRAF	AGTRAP-BRAF.A5B8.COSF828.1	Gene Fusion	BRAF Translocation	3
BRAF	AKAP9-BRAF.A7B11	Gene Fusion	BRAF Translocation	3
BRAF	AKAP9-BRAF.A21B10	Gene Fusion	BRAF Translocation	3
BRAF	AKAP9-BRAF.A22B9	Gene Fusion	BRAF Translocation	3
BRAF	AKAP9-BRAF.A28B9	Gene Fusion	BRAF Translocation	3
BRAF	AKAP9-BRAF.A8B9.COSF1013.1	Gene Fusion	BRAF Translocation	3
BRAF	AP3B1-BRAF.A22B9	Gene Fusion	BRAF Translocation	3
BRAF	ARMC10-BRAF.A4B11	Gene Fusion	BRAF Translocation	3
BRAF	ATG7-BRAF.A18B9	Gene Fusion	BRAF Translocation	3
BRAF	BAIAP2L1-BRAF.B12B9	Gene Fusion	BRAF Translocation	3
BRAF	BBS9-BRAF.B19B4	Gene Fusion	BRAF Translocation	3
BRAF	BCL2L11-BRAF.B3B10	Gene Fusion	BRAF Translocation	3
BRAF	BRAF-AP3B1.B8A23	Gene Fusion	BRAF Translocation	3
BRAF	BRAF-CIITA.B9C6	Gene Fusion	BRAF Translocation	3
BRAF	BRAF-MACF1.B8M15	Gene Fusion	BRAF Translocation	3
BRAF	BRAF-MRPS33.B1M2	Gene Fusion	BRAF Translocation	3
BRAF	BRAF-SLC26A4.B3S7	Gene Fusion	BRAF Translocation	3
BRAF	BRAF-SUGCT.B1S13	Gene Fusion	BRAF Translocation	3
BRAF	BTF3L4-BRAF.B3B11	Gene Fusion	BRAF Translocation	3
BRAF	C7orf73-BRAF.C2B9	Gene Fusion	BRAF Translocation	3
BRAF	CCDC6-BRAF.C1B9	Gene Fusion	BRAF Translocation	3
BRAF	CCDC91-BRAF.C11B9	Gene Fusion	BRAF Translocation	3
BRAF	CCNY-BRAF.C1B10	Gene Fusion	BRAF Translocation	3
BRAF	CDC27-BRAF.C16B9.1	Gene Fusion	BRAF Translocation	3
BRAF	CEP89-BRAF.C16B9	Gene Fusion	BRAF Translocation	3
BRAF	CLCN6-BRAF.C2B11.COSF1440	Gene Fusion	BRAF Translocation	3
BRAF	CLIP2-BRAF.C6B11	Gene Fusion	BRAF Translocation	3
BRAF	CUL1-BRAF.C7B9	Gene Fusion	BRAF Translocation	3
BRAF	CUX1-BRAF.C10B9	Gene Fusion	BRAF Translocation	3
BRAF	DYNC1I2-BRAF.D7B10	Gene Fusion	BRAF Translocation	3
BRAF	EML4-BRAF.E6B10	Gene Fusion	BRAF Translocation	3

Gene Name	Variant ID	Variant Type	Variant Description	Level of Evidence Code
BRAF	EPS15-BRAF.E22B10	Gene Fusion	BRAF Translocation	3
BRAF	ERC1-BRAF.E12B10	Gene Fusion	BRAF Translocation	3
BRAF	ERC1-BRAF.E17B8	Gene Fusion	BRAF Translocation	3
BRAF	FAM114A2-BRAF.F9B11	Gene Fusion	BRAF Translocation	3
BRAF	FAM131B-BRAF.F1B10.COSF1191	Gene Fusion	BRAF Translocation	3
BRAF	FAM131B-BRAF.F3B9.COSF1193	Gene Fusion	BRAF Translocation	3
BRAF	FAM131B-BRAF.F2B9.COSF1189.1	Gene Fusion	BRAF Translocation	3
BRAF	FCHSD1-BRAF.F13B9.COSF403	Gene Fusion	BRAF Translocation	3
BRAF	FXR1-BRAF.F13B10	Gene Fusion	BRAF Translocation	3
BRAF	GATM-BRAF.G2B11	Gene Fusion	BRAF Translocation	3
BRAF	GHR-BRAF.G1B10	Gene Fusion	BRAF Translocation	3
BRAF	GNAI1-BRAF.G1B10.COSF1442	Gene Fusion	BRAF Translocation	3
BRAF	GTF2I-BRAF.G4B10	Gene Fusion	BRAF Translocation	3
BRAF	HERPUD1-BRAF.H4B7	Gene Fusion	BRAF Translocation	3
BRAF	KCTD7-BRAF.K3B8	Gene Fusion	BRAF Translocation	3
BRAF	KCTD7-BRAF.K4B8	Gene Fusion	BRAF Translocation	3
BRAF	KDM7A-BRAF.K11B11	Gene Fusion	BRAF Translocation	3
BRAF	KIAA1549-BRAF.K9B9	Gene Fusion	BRAF Translocation	3
BRAF	KIAA1549-BRAF.K12B9.COSF1474	Gene Fusion	BRAF Translocation	3
BRAF	KIAA1549-BRAF.K12B11	Gene Fusion	BRAF Translocation	3
BRAF	KIAA1549-BRAF.K13B9	Gene Fusion	BRAF Translocation	3
BRAF	KIAA1549-BRAF.K14B9.COSF483	Gene Fusion	BRAF Translocation	3
BRAF	KIAA1549-BRAF.K14B11.COSF1226	Gene Fusion	BRAF Translocation	3
BRAF	KIAA1549-BRAF.K16B10	Gene Fusion	BRAF Translocation	3
BRAF	KIAA1549-BRAF.K17B10.COSF509	Gene Fusion	BRAF Translocation	3
BRAF	KIAA1549-BRAF.K18B9.COSF511	Gene Fusion	BRAF Translocation	3
BRAF	KIAA1549-BRAF.K15B9.COSF481.1	Gene Fusion	BRAF Translocation	3
BRAF	KIAA1549-BRAF.K15B10.COSF1283.1	Gene Fusion	BRAF Translocation	3
BRAF	KIAA1549-BRAF.K15B11.COSF485.1	Gene Fusion	BRAF Translocation	3
BRAF	KLHL7-BRAF.K5B9	Gene Fusion	BRAF Translocation	3

Gene Name	Variant ID	Variant Type	Variant Description	Level of Evidence Code
BRAF	LSM12-BRAF.L3B9	Gene Fusion	BRAF Translocation	3
BRAF	LSM14A-BRAF.L9B9	Gene Fusion	BRAF Translocation	3
BRAF	MACF1-BRAF.M60B9	Gene Fusion	BRAF Translocation	3
BRAF	MAD1L1-BRAF.M16B9	Gene Fusion	BRAF Translocation	3
BRAF	MAD1L1-BRAF.M17B10	Gene Fusion	BRAF Translocation	3
BRAF	MKRN1-BRAF.M4B9	Gene Fusion	BRAF Translocation	3
BRAF	MKRN1-BRAF.M4B11.COSF1444	Gene Fusion	BRAF Translocation	3
BRAF	MYRIP-BRAF.M16B9	Gene Fusion	BRAF Translocation	3
BRAF	MZT1-BRAF.M2B11	Gene Fusion	BRAF Translocation	3
BRAF	NUB1-BRAF.N3B9	Gene Fusion	BRAF Translocation	3
BRAF	NUDCD3-BRAF.N4B9	Gene Fusion	BRAF Translocation	3
BRAF	NUP214-BRAF.N21B10	Gene Fusion	BRAF Translocation	3
BRAF	PAPSS1-BRAF.P5B9.1	Gene Fusion	BRAF Translocation	3
BRAF	PLIN3-BRAF.P1B9	Gene Fusion	BRAF Translocation	3
BRAF	RAD18-BRAF.R7B10	Gene Fusion	BRAF Translocation	3
BRAF	RBMS3-BRAF.R11B11	Gene Fusion	BRAF Translocation	3
BRAF	RNF11-BRAF.R1B11	Gene Fusion	BRAF Translocation	3
BRAF	RNF130-BRAF.R3B9.COSF1483	Gene Fusion	BRAF Translocation	3
BRAF	RP2-BRAF.R3B10	Gene Fusion	BRAF Translocation	3
BRAF	SLC12A7-BRAF.S17B11	Gene Fusion	BRAF Translocation	3
BRAF	SLC45A3-BRAF.S1B8.COSF871	Gene Fusion	BRAF Translocation	3
BRAF	SND1-BRAF.S9B2	Gene Fusion	BRAF Translocation	3
BRAF	SND1-BRAF.S9B9	Gene Fusion	BRAF Translocation	3
BRAF	SND1-BRAF.S10B9	Gene Fusion	BRAF Translocation	3
BRAF	SND1-BRAF.S10B11	Gene Fusion	BRAF Translocation	3
BRAF	SND1-BRAF.S11B11	Gene Fusion	BRAF Translocation	3
BRAF	SND1-BRAF.S14B9	Gene Fusion	BRAF Translocation	3
BRAF	SND1-BRAF.S14B11	Gene Fusion	BRAF Translocation	3
BRAF	SND1-BRAF.S18B10	Gene Fusion	BRAF Translocation	3
BRAF	SND1-BRAF.S16B9.1	Gene Fusion	BRAF Translocation	3
BRAF	SOX6-BRAF.S5B9	Gene Fusion	BRAF Translocation	3
BRAF	SOX6-BRAF.S6B9	Gene Fusion	BRAF Translocation	3
BRAF	STRN3-BRAF.S3B10	Gene Fusion	BRAF Translocation	3
BRAF	TANK-BRAF.T4B9	Gene Fusion	BRAF Translocation	3
BRAF	TAX1BP1-BRAF.T8B11.1	Gene Fusion	BRAF Translocation	3
BRAF	TMEM178B-BRAF.T2B9	Gene Fusion	BRAF Translocation	3
BRAF	TMPRSS2-BRAF.T3B11	Gene Fusion	BRAF Translocation	3

Gene Name	Variant ID	Variant Type	Variant Description	Level of Evidence Code
BRAF	TRIM4-BRAF.T6B10	Gene Fusion	BRAF Translocation	3
BRAF	TRIM24-BRAF.T3B10	Gene Fusion	BRAF Translocation	3
BRAF	TRIM24-BRAF.T3B11	Gene Fusion	BRAF Translocation	3
BRAF	TRIM24-BRAF.T5B8	Gene Fusion	BRAF Translocation	3
BRAF	TRIM24-BRAF.T10B9	Gene Fusion	BRAF Translocation	3
BRAF	TRIM24-BRAF.T11B2	Gene Fusion	BRAF Translocation	3
BRAF	TRIM24-BRAF.T9B9.1	Gene Fusion	BRAF Translocation	3
BRAF	UBN2-BRAF.U3B11	Gene Fusion	BRAF Translocation	3
BRAF	ZC3HAV1-BRAF.Z3B10	Gene Fusion	BRAF Translocation	3
BRAF	ZC3HAV1-BRAF.Z7B11	Gene Fusion	BRAF Translocation	3
BRAF	ZKSCAN5-BRAF.Z2B9	Gene Fusion	BRAF Translocation	3
BRAF	ZSCAN30-BRAF.Z3B10	Gene Fusion	BRAF Translocation	3

Other BRAF Fusion events or novel BRAF activating mutations not listed in the above table but identified by one of the designated outside laboratories as described in the MATCH Master Protocol will also be considered actionable mutations (aMOIs) at Level of Evidence Code 3. Please refer to Section 1.4.2 of the MATCH Master Protocol for more information.

**Molecular Analysis for Therapy Choice (MATCH)
MATCH Treatment Subprotocol R: Trametinib**

Appendix III

Trametinib Ophthalmic Exam Form

Rev. 8/15

Subject Name: _____

Note to examiner: Please assess particularly for visible retinal pathology.

***Optical coherence tomography is highly recommended.** For patients in whom retinal abnormalities are noted, **color fundus photos, and fluorescein angiography if clinically indicated, are recommended.**

OPHTHALMIC EXAMINATION			
1. Date of Examination:	
 __/__/____ dd / mmm / yyyy 
		
VISUAL ACUITY			
Enter corrected visual acuity	OD:	OS:	
TONOMETRY			
Enter IOP (mmHg)	OD:	OS:	
INDIRECT FUNDOSCOPY			
Indirect Exam: Indicate normal or specify abnormalities	OD:	OS:	
CONFRONTATION VISUAL FIELD EXAM OR AUTOMATED PERIMETRY (e.g., Humphrey 24-2 or 30-2 or equivalent if using a non-Humphrey instrument)			
Indicate normal or specify any abnormalities	OD:	OS:	
OPTICAL COHERENCE TOMOGRAPHY (strongly recommended)			
Indicate normal or specify any abnormalities	OD:	OS:	
COLOR FUNDUS PHOTOS (recommended if retinal abnormalities are noted)*			
Indicate normal or specify any abnormalities	OD:	OS:	
FLORESCEIN ANGIOGRAPHY (suggested if retinal abnormalities are noted and test clinically indicated)*			
Indicate normal or specify any abnormalities	OD:	OS:	
Were any of the following noted on ocular history or exam?			
• History of CSR?		Yes	No
• Evidence of new optic disc cupping?			
• Evidence of new visual field defects?			
EXCLUSION CRITERIA			
• History of RVO?		Yes	No
○ If yes, patient is not eligible for the study.			

Signature of Examiner: _____

Printed Name: _____ Date: _____

**Molecular Analysis for Therapy Choice (MATCH)
MATCH Treatment Subprotocol R: Trametinib**

Rev. 8/15

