TREATMENT SUBPROTOCOL CO-CHAIR

[name]
Division of Hematology/Oncology
Department of Medicine
Wilmot Cancer Institute
[name]
[name]
[name]
[contact]
Email: [contact]

TRANSLATIONAL CHAIR

[name], PhD
Memorial Sloan Kettering Cancer Center
[name]
[name]
[contact]
E-mail: [contact]

Schema

Cycle = 28 days
Accrual Goal: 35

*

1. Introduction

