1.1.3 Safety

The adverse events (AEs) observed in the pivotal, Phase III registration study of trametinib in BRAF^{V600} mutant melanoma [5] were consistent with that seen across trametinib monotherapy studies and is summarized here. The Phase III study demonstrated that the 2 mg, continuous, once daily dose of trametinib has an acceptable safety profile. Adverse events occurring in ≥15% of subjects that received at least one dose of trametinib (N=211) were rash (57%), diarrhea (43%), peripheral edema (26%), fatigue (26%), dermatitis acneiform (19%), nausea (18%), alopecia (17%), and hypertension (15%). Less than 8% of the subjects had grade 3 or 4 rash (including only one patient with grade 4), and no grade 3 or 4 diarrhea was observed. Decreased ejection fraction or ventricular dysfunction occurred in 7% of the subjects, and <1% (n=2) had grade 3 cardiac-related events that were considered trametinib related and led to permanent discontinuation of the study treatment. Ocular events, most of which were grade 1 or 2, occurred in 9% of the subjects. Blurred vision was the most frequent ocular event (4%), and there was one case of reversible chorioretinopathy. Retinal vein occlusion, an AE that has been associated with MEK inhibitors, was observed only extremely rarely. Rash, diarrhea, visual disorders, hepatic disorders, cardiac-related AEs, and pneumonitis are considered AEs of special interest for trametinib because they are either known class effects (i.e., were observed with other MEK inhibitors) or are potentially life-threatening.

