MEK inhibitors have been associated with occasional responses in other cancers. In these studies, it is unclear whether BRAF non-V600 mutations or fusions were present. MEK inhibitors have been studied in advanced biliary tract cancer, notably a second line phase II trial with selumetinib. No BRAF^{V600E} mutations were found, however 12% of patients had a confirmed response and another 68% stable disease [23]. Selumetinib has also been investigated in non-small cell lung cancer (NSCLC). 87 patients were randomized to either selumetinib plus docetaxel or placebo plus docetaxel. There was a significant increase in progression free survival 5.3 months versus 2.1 months (HR 0.58 80% CI 0.42-0.79; p=0.014) and trend towards increased overall survival (9.4 months versus 5.2 months, HR 0.8-, 80% CI 0.56-1.14;p=0.21) in the selumetinib-containing arm [24]. A randomized phase II trial evaluated the MEK inhibitor AZD6244 versus pemetrexed in NSCLC. Among, 84 patients randomized, 2 patients in the AZD6244 arm had a partial response. Additional mutational analysis of the tumors was not available in this trial. Trametinib was evaluated in a phase 1 trial of advanced refractory solid tumors. Several patients experienced objective responses including two patients with pancreatic cancer (one with a KRAS mutation) and two with non-small cell lung cancer (NSCLC; both with KRAS mutations; one concurrently had a BRAF mutation) [3]. In addition, patients with colon, ovarian, and thyroid cancer also had some regression of their disease that did not reach a partial response. Of note, several patients harbored BRAF mutations although it was not reported whether these were V600 mutations. Another MEK inhibitor, BAY 86-9766, was evaluated as a single agent in a phase 1 trial, of 53 evaluable patients. One (colorectal) patient had a partial response, and 11 had stable disease [25].

2. Selection of Patients

Each of the criteria in the checklist that follows must be met, along with the eligibility in the MATCH Master Protocol, in order for a patient to be considered eligible for this study. Use the checklist to confirm a patient's eligibility. For each patient, this checklist must be photocopied, completed and maintained in the patient's chart.

In calculating days of tests and measurements, the day a test or measurement is done is considered Day 0. Therefore, if a test is done on a Monday, the Monday four weeks later would be considered Day 28.

ECOG-ACRIN Patient No. _____

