Patient's Initials (L, F, M) _____

Physician Signature and Date _____

NOTE: Policy does not allow for the issuance of waivers to any protocol specified criteria (http://ctep.cancer.gov/protocolDevelopment/policies_deviations.htm). Therefore, all eligibility criteria listed in Section 2 must be met, without exception. The registration of individuals who do not meet all criteria listed in Section 2 can result in the participant being censored from the analysis of the study, and the citation of a major protocol violation during an audit. All questions regarding clarification of eligibility criteria must be directed to the Group's Executive Officer ([contact]) or the Group's Regulatory Officer ([contact]).

NOTE: Institutions may use the eligibility checklist as source documentation if it has been reviewed, signed, and dated prior to registration/randomization by the treating physician.

NOTE: All patients must have signed the relevant treatment consent form

Rev. 8/15

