2.1 Eligibility Criteria

Rev.2/16

_____ 2.1.1 Patient must fulfill all eligibility criteria outlined in Section 3.1 of MATCH Master Protocol (excluding Section 3.1.6) at the time of registration to treatment step (Step 1, 3, 5, 7).

Rev. 8/15

Rev. Add13

_____ 2.1.2 Patients must have a BRAF non-V600 mutation or BRAF fusion, or another aberration, as identified via the MATCH Master Protocol and described in Appendix II. See [Appendix II](#) for information on the targeted mutations/fusions and the corresponding Levels of Evidence (LOE).

Rev. 8/15

_____ 2.1.3 Patients must have an electrocardiogram (ECG) within 8 weeks prior to treatment assignment and must have NONE of the following cardiac criteria:

- Clinically important abnormalities in rhythm, conduction or morphology of resting ECG (e.g. complete left bundle branch block, third degree heart block).
- Treatment-refractory hypertension defined as a blood pressure of systolic >140 mmHg and/or diastolic >90 mmHg which cannot be controlled by anti-hypertensive therapy.

3 Trametinib Treatment Plan

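### Is the exclusion for a history of retinal vein occlusion a gap in eligibility because it stands only on the eye-exam form?

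*Protocol*

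**What the plan says.** Appendix III of the protocol is a one-page form for the eye examiner. Its last block is headed as exclusion criteria and asks about a history of RVO, with the instruction "If yes, patient is not eligible for the study".

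Section 2 says where eligibility is decided: "Each of the criteria in the checklist that follows must be met, along with the eligibility in the MATCH Master Protocol". A note there adds that "Policy does not allow for the issuance of waivers to any protocol specified criteria". It then warns that "The registration of individuals who do not meet all criteria listed in Section 2 can result in the participant being censored from the analysis".

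Section 2.1 shows three items:

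- Item 2.1.1 brings in Section 3.1 of the Master Protocol, apart from its Section 3.1.6.
- Item 2.1.2 requires the BRAF aberration, "as identified via the MATCH Master Protocol and described in Appendix II".
- Item 2.1.3 covers the ECG and refractory hypertension.

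The Section 4.1 calendar marks an eye exam before registration. On treatment the exam is only as clinically indicated (footnote I). Section 3.4.4 lists the components of the eye exam and, in Table 4, the handling of RVO diagnosed on treatment.

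**The concern.** An eligibility rule ought to stand where eligibility is checked. Section 2 points sites to its own checklist and to the Master Protocol, and its warning about audit citations and censoring from the analysis is worded for criteria listed in Section 2. The RVO exclusion is on neither the visible checklist nor the calendar, and nothing in the text directs a site to Appendix III. Elsewhere the protocol does make such links. Item 2.1.2 cites Appendix II, and calendar footnote K repeats the 8-week ECG window of item 2.1.3.

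A site that completed the checklist and did the eye exam on its own paperwork could therefore register a patient whom the protocol's form calls ineligible. It would then be unclear whether the censoring sentence reaches that patient, and so whether the patient counts in the analysis.

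**Working it through.** The protocol states no figure on this point, so the check is a comparison of texts.

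**1. Every mention of RVO.**

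| Place | Content | Eligibility rule? |
|---|---|---|
| Section 1.1.3 | Background: "Retinal vein occlusion, an AE that has been associated with MEK inhibitors, was observed only extremely rarely" | No |
| Section 3.2.1 | Expedited reporting if diagnosed | No |
| Section 3.3 | Listed as rare but serious | No |
| Section 3.4.4, Table 4 | Management on treatment | No |
| Appendix III | History of RVO makes the patient ineligible | Yes |

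The rule is stated once. No second statement conflicts with it.

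**2. Every citation of an appendix.** Section 2.1.2 cites Appendix II of this subprotocol. Section 3.2.1 and calendar footnote E cite Appendices VIII and XII of the Master Protocol. Appendix III of this subprotocol is cited nowhere, so the missing pointer is real in the text at hand.

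**3. What a site does if it follows the plan.** The calendar requires an eye exam before registration. The note above the calendar places pre-registration assessments within 4 weeks of registration, excepting only imaging and the ECG, so the eye exam falls in that window. The protocol supplies one eye-exam form. A line declaring a patient ineligible makes sense only before registration, so the form itself shows that it is meant for that exam. Using it raises the RVO question. A yes excludes the patient, and the no-waiver sentence, which covers any criterion the protocol specifies, reaches an exclusion printed in its appendix.

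**4. Whether the checklist is really silent.** None of the three visible items names an eye condition, but item 2.1.1 is a pointer to an unknown number of Master Protocol criteria. A count of none out of three therefore does not describe the full eligibility rules. The copy at hand is also incomplete in at least one place: Section 1.2.1 breaks off in the middle of a list. The echocardiogram or nuclear study, likewise required before registration, has no visible checklist item either. That fits a design in which not every baseline test has its own item, and it also fits loss of later items from this copy.

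**5. Size.** The Schema gives "Accrual Goal: 35". One wrongly registered patient would be 1/35 = 2.9% of the cohort. The protocol gives no prevalence of prior RVO. Any assumed prevalence would yield the chance that a patient with such a history is among the 35. It would not yield the chance of a wrongful registration, because it ignores the required exam, the form and the Master Protocol.

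**The case for a change.** The strongest case for a change is that the form is loosely tied to the rest of the protocol. Section 3.4.4 includes slit-lamp biomicroscopy, for which the form has no field. The form also asks about new disc cupping and new field defects alongside the history question, so it does not say at which visit it is to be completed. Nothing shown obliges a site to use it at the baseline exam. RVO is treated categorically elsewhere: Table 4 calls for permanent discontinuation on an RVO diagnosis in every grade row. A site should not have to find an uncited page to learn of a related bar to entry, and a pointer would cost one line.

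The facts in this argument stand: the form is not cited, and a pointer would be tidy. The inference does not follow. An untidy form still states its exclusion without ambiguity, and silence in Section 2.1 is not a competing rule. For harm to follow, a site would have to do the required exam, leave the supplied form unused and miss the history, and Master Protocol Section 3.1 would have to lack a matching criterion. The doubt about the censoring sentence is narrow too. That sentence says such a registration can lead to censoring, not that it must, and the handling of ineligible patients in the analysis may properly sit in the Master Protocol or an analysis plan.

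**Conclusion.** The observation is correct for the text at hand, but it does not show an error in the plan. The exclusion is stated once and clearly, the exam at which it applies is already required before registration, and no other passage contradicts it. What is missing is an editorial cross-reference that sites can supply by using the form provided. It changes no sample size, error rate, endpoint or analysis rule. One affected patient would be 2.9% of the accrual goal, and the document offers no basis for a probability.

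This rests on two assumptions: that sites use the protocol's own form for the required baseline eye exam, and that the no-waiver sentence is read on its plain words as covering the appendix. Master Protocol Section 3.1 and the complete source of Section 2.1 were not available. If either holds the criterion, even the cross-reference point largely disappears. No view is taken on what the eligibility rule should be.
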